2.1.2 Known Potential Benefits

The potential benefits of the proposed research include: 1) a significant decrease in suicidal ideation and depressive symptoms, 2) significantly fewer memory impairments with MST compared to ECT, 3) faster recovery or orientation immediately following treatment with MST versus ECT. Our preliminary data suggests response rates of over 50 percent and extensive research on ECT has illustrated a remission rate of between 50-75 percent.

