- (1) Test of Premorbid Function (TOPF)[83] - measures premorbid IQ - baseline only
- (2) Montreal Cognitive Assessment (MoCA)[70, 84] - measures global cognitive function – baseline, end of treatment, follow-up
- (3) three tests from the Delis Kaplan Executive Function System (D-KEFS)[85]: Verbal Fluency, Color-Word Interference, and Tower Test—measures executive functions including verbal fluency, inhibition, cognitive flexibility, and planning—baseline, end of treatment, follow-up
- (4) California Verbal Learning Test- Third Edition (CVLT-3)[86] - measures verbal learning and memory, and effort – baseline, end of treatment, follow-up
- (5) Autobiographical Memory Test (AMT)[87] - measures autobiographical memory recall and specificity – baseline, end of treatment, follow-up
- (6) NIH Toolbox: Flanker Test, Picture Sequence Test, List Sorting Working Memory Test [88]—measures processing speed, attention, visuospatial memory, and working memory—baseline, end of treatment, follow-up
- (7) Time to Reorientation (as used in the PRIDE Study) [89, 90] - measures reorientation time – after the first three treatments

These assessments will be completed upon participant termination of treatment, including both completion of the treatment course or withdrawal from treatment prior to completion.

The specific cognitive measures included in this battery were selected based on the need for 1) measures of global cognitive function and estimated intellectual ability in statistical models, 2) psychometrically sound cognitive measures, 3) cognitive measures with normative data and alternate forms to minimize confounding demographic and practice effects, and 4) maximizing cognitive measurement while minimizing participant burden.

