5.2 Interventions

5.2.1 General Anesthesia: At all sites, treatment with MST or RUL-UB ECT will be provided by trained study psychiatrists and will follow standard protocols. Stimulation will be provided two or three times a week under general anesthesia. Anesthesiologists experienced in ECT will administer general anesthesia using methohexital or etomidate, muscle relaxation using

succinylcholine and mask ventilation with 100% oxygen. For patients with inadequate seizures with methohexital as the induction agent, as determined by the study psychiatrist, the anesthetic agent will be switched to etomidate. Monitoring of blood pressure, oxygen saturation, heart rate and EKG will be conducted throughout the course of the procedures. All medications listed above will be used at doses within labeling.

5.2.2 Determination of Seizure Threshold at the First Session: Following a standard established protocol [91], a study psychiatrist will determine the seizure threshold during the first treatment session. The seizure threshold represents the minimum energy required to achieve a generalized tonic-clonic seizure; it is determined only during the first treatment session and the energy used during subsequent sessions is based on this threshold. Glycopyrrolate IV may be used during seizure titration as subthreshold stimulations with either ECT or MST may result in a marked bradycardia or asystole [92]. Glycopyrrolate will be used at doses within labeling.

5.2.3 Medications for MST or ECT Related Side Effects: Medications that may be used to treat MST or ECT related side effects include, but are not limited to: granisetron, ondansetron or dymenhydrinate for nausea, ketorolac, acetaminophen, ibuprofen for headaches or muscle pain and esmolol or labetalol for treatment related hypertension. Prolonged seizures (i.e., seizures longer in duration than two minutes as recorded either through EEG (spike-wave complexes) or through prolonged tonic-clonic muscular activity) will be treated with either repeat administration of the anesthetic (i.e., methohexital) or midazolam. Midazolam should be used as judiciously as possible owing to its potential to prolong reorientation times after treatment. All medications listed above will be used at doses within labeling.

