5.2.4 Monitoring and Seizure Adequacy: During all sessions, the seizure quality will be monitored using fronto-mastoid electroencephalography (EEG). Congruent with published criteria, seizures will be considered adequate if they result in generalized tonic-clonic activity ≥ 15 seconds of motor tonic-clonic activity [76, 93, 94], which includes the duration of the stimulus[95]. The anaesthetics dosing and MST or ECT parameters will be reviewed and optimized in the event of inadequate seizures.

5.2.5 Treatment Parameters: MST treatments will be administered using the MagPro XP with a twin coil. Stimulation will be delivered over the frontal cortex at the midline position directly over the electrode FZ according to the international 10-20 system[96, 97]. The twin coil produces seizures that are comparable to those produced with ECT[8]. Frontal stimulation is an advancement over previous studies by delivering convulsive stimuli to frontal brain regions[98-100]. The MST determination of seizure threshold will be done using 100% machine output applied at 100 Hz at progressively escalating train durations, commencing at 2 seconds and increasing by 2 seconds with each subsequent stimulation until an adequate seizure is produced (Section 5.2.5). During subsequent sessions, one stimulation will be delivered using a train duration that is 4 seconds longer than the train duration at threshold (with a maximum train duration of 10 seconds). For instance, if the threshold train duration is 4 seconds, subsequent stimulations will be delivered with a train duration of 8 seconds.

ECT treatments will be administered using the MECTA spECTrum 5000Q or the MECTA Sigma devices. The ECT determination of seizure threshold and the adjustment of energy at subsequent sessions will be based on a standard published protocol [10]. All participants will receive RUL-UB ECT at six times the seizure threshold. This approach follows the standard of previous ECT trials [9, 76].

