5.8.3 Adverse Event Analysis

The analysis of all adverse events will include incidence tables by severity, relationship to treatment and baseline parameters. Adverse event rates will be compared between the study groups:

- a. Compare average number of items endorsed on the Columbia ECT Side Effects Schedule between groups after treatment. We anticipate that there will be no significant differences in side effects between these two treatments and will conduct comparisons of safety endpoints at trial conclusion.
- b. Compare AE's between groups
 1. Absolute count of AE experienced during treatment course in both groups
 2. Mean headache score for treatment course
 3. Mean nausea score

4. Mean dizziness
 5. Mean pain
 6. Mean number of treatments with presence of post-ictal confusion or agitation
 7. Mean other AE's
 8. Absolute count of dropout between groups
 9. Absolute count of SAE's between groups
- c. Time to reorientation: 1) Compare the average number of participants between ECT and MST who achieved reorientation within a certain time frame across the first three treatments. 2) Compare the proportion of patients who achieve reorientation between the ECT and MST conditions at treatment sessions one, two, and three.

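### Time to reorientation is analysed as counts within an undefined window and a proportion with no stated limit, so the claimed shortening of disorientation is never estimated in minutes

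*Combined protocol and SAP*

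**What the plan says.** Section 5.1.5 lists "Time to Reorientation (as used in the PRIDE Study" among the cognitive measures, to be taken after the first three treatments. The procedure is given only by reference to that other trial. No observation limit or criterion is restated.

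Section 5.8.3 item c is the only analysis text. Its first comparison is between the arms' average numbers of participants "who achieved reorientation within a certain time frame across the first three treatments". Its second is "Compare the proportion of patients who achieve reorientation between the ECT and MST conditions at treatment sessions one, two, and three". Item c names no test, no model for repeated sessions, and no rule for participants who have not reoriented when observation ends.

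The first of the three sessions is the one in which seizure threshold is found. Section 5.2.2 says of the threshold that "it is determined only during the first treatment session and the energy used during subsequent sessions is based on this threshold". For MST, Section 5.2.5 describes trains "increasing by 2 seconds with each subsequent stimulation until an adequate seizure is produced".

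Section 2.1.2 lists among the potential benefits "faster recovery or orientation immediately following treatment with MST versus ECT", and Section 4.0 also presents a shorter period of disorientation as a gain for patients. Section 3.0 does not include reorientation in the primary, secondary or tertiary hypotheses. Section 8.7 makes the measure optional under the COVID-19 procedures and notes that it is not a primary outcome.

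**The concern.** The quantity collected is a duration, and the benefit claimed is a shorter duration, yet both planned comparisons turn it into a yes/no result. Three consequences follow.

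- **No estimate on the scale of the claim.** Neither comparison yields minutes or a ratio of times, so the result cannot be set beside the minutes that Section 1.1.3 cites from an earlier 20-patient comparison.
- **An open cut-off.** The window in the first comparison is undefined. The second either has no window or borrows the same undefined one. Safety comparisons are made at trial conclusion, so nothing in these documents stops the window being chosen once the data are visible.
- **Lost information.** A cut discards part of the information in the times. How much depends on where the cut falls and how large the true difference is.

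The first comparison also merges the titration session with the two that follow, so any difference between the sessions is hidden there.

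**Working it through.** The plan states no window, test or power for this measure, so there is no figure of its own to reproduce. What follows is illustration under stated assumptions.

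**Inputs from the documents:** 130 per arm (Section 5.7.1); 4 versus 18 minutes for MST and ECT, with no SD given (Section 1.1.3); disorientation of up to 40 minutes after ECT (Section 1.1.2).

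**Inputs assumed:** two-sided 5% test; a smaller effect of 12 versus 18 minutes; 65 per arm as a low case for an optional measure; exponential or log-normal times as stated.

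**1. Information kept by a cut.** For normal log-times and a modest difference, relative efficiency = φ(c)² / [p(1 − p)], where p is the share reoriented by the cut and c the matching normal quantile.
- p = 0.5: 0.3989² / 0.25 = 0.637
- p = 0.8: 0.2800² / 0.16 = 0.490
- p = 0.9: 0.1755² / 0.09 = 0.342

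**2. Power at the cited effect.** With exponential times of mean m, the share reoriented by window w is 1 − exp(−w/m). Power for two proportions uses the pooled variance under the null and the unpooled variance under the alternative. For means of 4 and 18 minutes at w = 40, the shares are 1.000 and 0.892.

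| Window (min) | 130 per arm | 65 per arm |
|---|---|---|
| 5-20 | about 100% | 99.9% or more |
| 30 | about 100% | 96.4% |
| 40 | 97.5% | 78.5% |
| 60 | 58.5% | 33.5% |
| 90 | 15.3% | 9.7% |

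**3. Power at a smaller effect.** For 12 versus 18 minutes with every time observed, the full-time analysis has √(260/4) × ln(18/12) = 8.062 × 0.4055 = 3.269, and 3.269 − 1.960 = 1.309, giving 90.5% power at 130 per arm. Information kept is the squared ratio of (normal quantile of power + 1.960) to 3.269.

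| Window (min) | Share MST / ECT | Power, 130 per arm | Information kept |
|---|---|---|---|
| 5 | 0.341 / 0.243 | 41.3% | 28% |
| 20 (best tried) | 0.811 / 0.671 | 73.6% | 63% |
| 60 | 0.993 / 0.964 | 36.6% | 24% |
| 90 | 0.999 / 0.993 | 12.8% | 6% |

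At 65 per arm the full-time analysis has 63.7% power and the 20-minute window 44.6%.

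**4. No limit in the second comparison.** In both exponential cases 96-100% have reoriented by 60 minutes and over 99% by 90 minutes. A proportion with no limit therefore approaches 100% in each arm, with almost nothing left to compare.

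**5. Choosing the window afterwards.** Simulation with no true difference: 10,000 runs, 130 per arm, log-normal times with median 15 minutes and log-SD 0.8, correlation 0.5 between sessions, windows of 5, 10, 15, 20, 30 and 40 minutes. The chance of at least one p < 0.05 is:
- one fixed window, one session: about 5.5%
- six windows, one session: about 22%
- one window, three sessions: about 15%
- six windows, three sessions: about 48%

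**The case against.** A reader might infer that the plan tests a key benefit with too little information to detect it. At the documents' own figure that does not hold: step 2 shows a fixed window of 5-40 minutes retaining at least 97% power at 130 per arm. The 4 versus 18 minutes came from 20 openly allocated patients, so a smaller effect is possible, but a serious loss needs a smaller effect, a badly placed window or fewer measurements.

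A reader might also infer that the second comparison certainly has no window. It stands under the same heading as the first and may be its per-session form with the same window. That reading removes the near-100% problem but leaves the window undefined.

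Nor do the documents support the view that including titration biases the comparison. Both arms are titrated in the first session, and the second comparison is made by session, so only the first comparison merges them. Dropping session 1 from the main contrast would change the question asked and discard data, so it is not proposed here.

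The trial cited in Section 5.1.5 may fix a limit; these documents do not restate one. Item c is silent on a model, and silence does not show that correlation within participants would be ignored. Finally, the measure belongs to no formal hypothesis, and cognitive superiority rests on the AMT.

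These points limit the size of the problem. They do not supply the window or an estimate in minutes.

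**Conclusion.** The point holds in limited form. A recorded time is reduced to a count within an undefined window and a proportion with no stated limit, and the claimed shortening of disorientation is not estimated. For modest differences and roughly log-normal times, a cut keeps about 64%, 49% or 34% of the information when 50%, 80% or 90% have reoriented by it. At 12 versus 18 minutes with exponential times, power falls from 90.5% to at most 73.6% among the windows tried. At 4 versus 18 minutes the loss is negligible for windows of 5-40 minutes with 130 per arm, though it returns at 65 per arm with a 40-minute window (78.5%). The simulated false-positive rates describe what an unfixed window permits; nothing in the documents shows that anyone intends to search for one.

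This is a minor, inexpensive improvement to a non-primary measure. The primary, secondary and tertiary conclusions do not depend on it.

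**What to change.** Replace item c of Section 5.8.3 with an analysis of recorded minutes to reorientation:

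- Treat the times from sessions 1-3 as time-to-event data, censored at the end of observation.
- Use a model that allows for repeated sessions within participant, for example a Cox or accelerated-failure-time model with frailty or robust variance, with arm, session and site.
- Report median times and the arm effect with a 95% CI, overall and by session, so that the titration session can be seen separately.
- If a proportion is kept as support, state its window, say that it applies to both summaries, and fix it before unblinding.

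The cost is new SAP wording and slightly more analysis. The time itself is already a planned measurement. The analysis also needs the time at which observation ended for anyone not reoriented; the documents do not say whether this is captured, so the case report form should be checked.

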5.8.4 Tertiary Outcome Analysis: Neurophysiological Data

We will investigate the relationship between change in CI and SSI reduction by calculating the area under the receiver operating characteristic (ROC) curve (AUC) as discussed above (Section 1.3.4). ROC analysis is used in medicine to evaluate diagnostic test accuracy. The ROC involves plotting the sensitivity (true positive rate) versus 1-specificity (false positive rate). The ROC AUC predicts performance of the diagnostic test. An AUC of 1 represents perfect prediction with optimal sensitivity and specificity while 0.5 suggests that the diagnostic test is no better than chance at diagnostic prediction. For our purposes, the ROC AUC then corresponds to the change in CI that optimally distinguishes MST and ECT remitters from non-remitters (defined as a zero score on the SSI). Based on our preliminary data described above (Section 1.3.4), we will use change in CI (defined as the LICl TMS-EEG response) to distinguish MST and ECT SSI remitters from non-remitters using a ROC AUC of >0.85 on all frontal electrodes using a false detection rate correction that is applied to all frontal electrodes.

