The proposed study will employ a relatively new approach to delivering ECT through right unilateral electrode placement combined with ultrabrief pulse width (RUL-UB ECT; 0.3 msec). Animal and human studies have demonstrated that ultrabrief pulse widths induce more efficient seizures compared to standard pulse widths (0.5 to 1 msec)[28]. When applied at six times the seizure threshold, RUL-UB ECT was shown to be as effective as standard pulse width RUL ECT but with significantly fewer and more attenuated cognitive adverse effects[10]. Although RUL-UB ECT does seem to reduce cognitive adverse effects, a greater number of treatments are required to produce comparable therapeutic effects to standard pulse width ECT[29-31] with increased cognitive impairments emerging after more treatment. Thus, patients treated with RUL-UB ECT still experience significant memory impairment compared to baseline.

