5.0 APPROACH

5.1.1 Research Design and Methods

The trial will be registered in an international clinical trial registry (clinicaltrials.gov) and results will be reported in a manner consistent with the international CONSORT guidelines. The study will involve a randomized, double blind, parallel-group clinical trial with two treatment arms conducted at three leading academic institutions in North America: CAMH, University of Texas Southwestern in Dallas, and University of California, San Diego (UCSD). Based on our power analysis (Section 5.7.1), a total of 260 participants with depression will be randomized to receive MST or RUL-UB-ECT. We plan to enroll four to five participants per month across the three study sites over 54 months.

Treatment will be administered two to three days per week. Depression symptoms will be assessed with the 24-item Hamilton Depression Rating Scale (HRSD-24) [74] and suicidality will be assessed with the Scale for Suicidal Ideation (SSI) [69]. Remission will be defined as HRSD-24 ≤ 10 and a $> 60\%$ decrease in scores from baseline on two consecutive ratings. Once a participant reaches remission, a second rating to confirm remission will be conducted immediately before their next scheduled treatment. If remission is confirmed, they will then be considered a completer of the acute treatment course. Remission of suicidal ideation is defined as a score of 0 on the SSI. Therefore, there will be no specific minimum number of treatments that patients must receive to be classified as remitters. However, patients who do not meet remission criteria after 21 treatment sessions will be considered non-remitters and will cease treatment sessions. This maximum treatment number was chosen allowing for the possibility that MST may require more treatment sessions to achieve remission, similar to RUL-UB ECT [29-31]. The blind will not be broken to participants until the completion of the entire study. Following completion of the acute treatment course, participants who achieve response (defined as a 50% reduction in symptoms on the HRSD-24 from baseline) or remission will be referred to a maintenance treatment trial.

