5.3 Neurophysiological Indices of Cortical Inhibition in the DLPFC

TMS-EEG will be used to evaluate neurophysiological measures from the DLPFC prior to and after a course of either ECT or MST treatment. TMS will be administered to the left DLPFC using two Magstim-200 stimulators (Magstim Company Ltd., UK) connected via a Bistim module and electrophysiological data will be collected using dedicated hardware and software (Neuroscan, Compumedics, USA). Each TMS session will include the establishment of the individual threshold for stimulation, followed by cortical inhibition paradigms in the DLPFC according to our previously published methods [63]. Identification of the DLPFC will be conducted in a manner that is identical to those during rTMS treatment. Recordings will be acquired through a 64-channel electroencephalography (EEG). Neurophysiological indices from the DLPFC (e.g., N100 and LIC1) will be the dependant variables of interest and derived according to previous publications [63, 66]. Prior to study start, the teams at UT Southwestern and UCSD will set up a laboratory with the necessary equipment and materials, and will be trained on the methods of the proposed experiment. A neurophysiology expert from the Temerty Centre at CAMH will be visiting UT Southwestern and UCSD to ensure that the TMS-EEG recordings are compatible between sites.

Variability between sites is low as previous trials between CAMH and Melbourne, Australia have shown comparable measures between these three sites. Neurophysiological data will be collected and coded by experienced raters who will be blind to treatment status. Data analysis will take place at CAMH using semi-automated methods developed and validated by our group.

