5.4. Resting EEG and Multi-Scale Entropy

Ten minutes of resting-state eyes closed EEG data are recorded prior to the start and after a course of ECT or MST treatment. EEG will be through a 64-channel NeuroScan EEG system. Acquired data will be imported into MATLAB (The MathWorks. Inc. Natick, MA, USA) for preprocessing. The open source signal processing functions in EEGLAB toolbox will be used for data import and preprocessing. Multi-scale entropy will be examined across all electrodes using two steps [101]: The *coarse-graining* process and the calculation of the sample entropy (*SampEn*) for each coarse-grained time series. First, for a given time series $\{x_1, x_2, \dots, x_N\}$, the multiple coarse-grained time series $\{y_1^{(\tau)}, y_2^{(\tau)}, \dots, y_N^{(\tau)}\}$ at scale factor τ are calculated by averaging the data points within non-overlapping windows of increasing length τ . Each element of the coarse-grained time series $y_j^{(\tau)}$, will be calculated as $y_j^{(\tau)} = \frac{1}{\tau} \sum_{i=(j-1)\tau+1}^{j\tau} x_i$, where τ represents the scale factor and $j \left(1 \leq j \leq \frac{N}{\tau}\right)$ represents the time index of the element. The length of each coarse-grained time series is M , where $M = \text{floor} \left(\frac{N}{\tau}\right)$. Second, the degree of predictability is measured for each of the multiple coarse-grained time series $\{y_1^{(\tau)}, y_2^{(\tau)}, \dots, y_N^{(\tau)}\}$ using SampleEn. SampleEn is calculated as $\text{SampleEn}(r, m, M) = -\ln(C(m+1)/C(m))$, where $C(m)$ is the total number of pairs of m consecutive similar data points, $C(m+1)$ is the total number of pairs of $m+1$ consecutive similar data points in the multiple coarse-grained time series. SampleEn quantifies the variability by estimating the predictability of amplitude patterns across a time series. Two consecutive data points will be used for data matching ($m = 2$) and data points will be considered to match if their absolute amplitude difference is less than 0.15% ($r = 0.15$) of standard deviation of time series. Multi-scale entropy will be calculated for two 20s continuous epochs according to Farzan et al. and then averaged [102].

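### The LICI-change analysis pools patients whose second recording follows very different numbers of sessions, so treatment exposure alone could give a significant, though moderate, association with SSI remission

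*Combined protocol and SAP*

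**What the plan says.** **Analysis.** Section 5.8.4 states: "We will investigate the relationship between change in CI and SSI reduction by calculating the area under the receiver operating characteristic (ROC) curve (AUC". The predictor is the change in LICI. The classes are SSI remitters and non-remitters, with MST and ECT taken together, and section 5.1.1 fixes the class: "Remission of suicidal ideation is defined as a score of 0 on the SSI". The stated level is an AUC above 0.85, with a multiplicity correction over frontal electrodes. No covariate is named. Tertiary hypothesis (1) in section 3.0 concerns MST only and asks for significant prediction, with no AUC level.

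**Timing.** Section 5.3: "TMS-EEG will be used to evaluate neurophysiological measures from the DLPFC prior to and after a course of either ECT or MST treatment". Table 1 in Appendix A places TMS/EEG at baseline and in the post-acute phase only. Resting EEG is likewise "recorded prior to the start and after a course of ECT or MST treatment" (section 5.4).

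**Course length.** Section 5.1.1 stops treatment on the HRSD-24: "If remission is confirmed, they will then be considered a completer of the acute treatment course". It adds that "there will be no specific minimum number of treatments that patients must receive to be classified as remitters", while "patients who do not meet remission criteria after 21 treatment sessions will be considered non-remitters and will cease treatment sessions". Section 5.2.5 raises the stimulus in patients who have not improved enough by treatments 6, 9 and 12. Sessions are given two or three times a week, so the interval between recordings varies too.

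**Entropy.** Section 5.8.5 bases its ROC on entropy at baseline. Tertiary hypothesis (2) concerns an increase in complexity after treatment. Treatment duration enters the analysis plan only as a variable in the imputation model of section 5.8.1.

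**The concern.** The second recording is not taken at a common point. It is taken when treatment stops, and stopping depends on response. A patient who remits early has few seizures, few anaesthetics and a short interval between recordings. A patient who does not remit may have 21 sessions and a higher stimulus.

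If LICI drifts with exposure, and if SSI and HRSD-24 remission are associated, LICI change will differ between SSI classes even when cortical inhibition has no bearing on suicidal ideation. Pooling MST and ECT adds a further route, since section 5.1.1 allows that MST may need more sessions.

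At stake is the reading of the result. A significant association would be presented as evidence that changing inhibition relieves suicidal ideation, when it might reflect only who was treated longer. The bias can also run against a true effect, because 5.8.4 states no expected direction for LICI change.

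**Working it through.** **The plan's figure.** The only sample size, 260, is for HRSD-24 non-inferiority. It reproduces at one-sided 0.05 with variance at 0.50 and 0.35: Φ(0.15/√((0.25 + 0.2275)/130) − 1.645) = Φ(0.83) = 0.80. The biomarker aims have no calculation of their own.

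**Inputs from the documents.** HRSD-24 remission 50% (5.7.1); remission about 60% (5.8.2, taken here as the SSI rate, although the text names no scale); no minimum number of sessions, maximum 21 (5.1.1).

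**Assumptions, not in the documents.**
- HRSD-24 remitters finish at 4, 7, 10, 13, 16 or 19 sessions, equally likely (mean 11.5, variance 26.25). Non-remitters have 21, or 20% of them stop sooner.
- P(SSI = 0) with and without HRSD-24 remission is a/b: 0.8/0.4 or 0.9/0.3, both giving 60% overall.
- LICI change correlates ρ with session count and has no other link to SSI.

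**Step 1, exposure by SSI class, at 0.9/0.3.** Of SSI remitters, 0.45/0.60 = 75% are HRSD-24 remitters; of SSI non-remitters, 0.05/0.40 = 12.5%. Mean sessions are 0.75 × 11.5 + 0.25 × 21 = 13.9 against 0.125 × 11.5 + 0.875 × 21 = 19.8.

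**Step 2, AUC of session count alone.** Counting ties as half: 0.75 × 0.125 × 0.5 + 0.75 × 0.875 + 0.25 × 0.875 × 0.5 = 0.81. At 0.8/0.4 the same sum gives 0.71.

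**Step 3, AUC of a LICI change that reflects exposure only.** The session variance is 0.5 × 26.25 + 0.25 × 9.5² = 35.69, so the SD is 5.97. For two patients differing by D sessions, the chance of correct ordering is Φ(ρD / (5.97√(2(1 − ρ²)))). With ρ = 0.5 this is Φ(0.0683 D). Against a 21-session patient, D is 17, 14, 11, 8, 5 or 2, and the mean probability is 0.730. The AUC at 0.9/0.3 is 0.75 × 0.125 × 0.5 + 0.75 × 0.875 × 0.730 + 0.25 × 0.125 × 0.270 + 0.25 × 0.875 × 0.5 = 0.64.

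| SSI split a/b | Early stopping | ρ = 0.3 | ρ = 0.5 | ρ = 0.7 |
|---|---|---|---|---|
| 0.8/0.4 | none | 0.56 | 0.60 | 0.64 |
| 0.9/0.3 | none | 0.59 | 0.64 | 0.70 |
| 0.8/0.4 | 20% | 0.54 | 0.57 | 0.60 |
| 0.9/0.3 | 20% | 0.56 | 0.61 | 0.66 |

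If SSI and HRSD-24 remission are unrelated (0.6/0.6), every entry is 0.50.

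**Step 4, chance of nominal significance.** The null standard error of the AUC is √((n + 1)/(12 n₁n₀)). With n = 260 (156 and 104) it is 0.037; with n = 130 (78 and 52) it is 0.052. By simulation without early stopping, exposure alone reaches two-sided p < 0.05 at 0.9/0.3, ρ = 0.5 in 98% of trials of 260 and 81% of trials of 130. At 0.8/0.4, ρ = 0.3 the figures are 36% and 21%. These are single-test figures; correcting over electrodes controls chance findings, not a bias that the electrodes share.

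**Step 5, chance of passing 0.85.** At 0.9/0.3, ρ = 0.5 this is about 0% with 130 or 260 patients. A large-sample AUC above 0.85 needs near-complete agreement of the two remissions and ρ of about 0.9 or more (1.0/0.2 with ρ = 0.9 gives 0.854).

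**Step 6, entropy.** If sessions drive both entropy change and AMT decline, the spurious correlation is the product of the two links: 0.3 × 0.3 = 0.09 up to 0.7 × 0.7 = 0.49. The AUC for the worst 30% on the AMT is then 0.54 to 0.69 by simulation. With a baseline entropy value unrelated to exposure it is 0.50.

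**Step 7, does allowing for sessions discard a true marker?** Take a marker tied to SSI remission and independent of sessions given SSI, with true AUC 0.86 (standardised difference √2 × 1.08 = 1.53). In a logistic model with session count correctly represented, its coefficient stays 1.53, so its added value is visible. Residualising the marker on sessions does lose signal: the AUC falls to somewhere between 0.76 and 0.85, depending on how SSI, HRSD-24 and the marker are linked.

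**The case against.** The strongest reply is the plan's own threshold. Every AUC in the table is well under 0.85. A reader might infer that no positive ROC could be read as target engagement; the figures do not support that, because an AUC above 0.85 in a sample of the planned size could hardly come from exposure alone. This stands. It does not answer hypothesis (1), which has no AUC level and would be met by a significant AUC of 0.64.

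Second, the two links are assumed. No passage says that LICI moves with session count. The course ends on the HRSD-24 while the outcome is the SSI, and section 1.2.1 suggests that suicidal ideation may respond to ECT more than depressive symptoms do. This also stands: the bias is possible, not shown. Some association between the two scales in one depressed sample is nevertheless likely, and section 1.3.4 itself proposes that MST modifies LICI.

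Third, a reader might extend the point to the ROC in 5.8.5, since section 1.1.2 describes RUL-UB ECT "with increased cognitive impairments emerging after more treatment". That ROC uses a baseline value, which later sessions cannot alter. Only an entropy-change analysis is exposed.

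Fourth, session count is partly a result of response, so adjustment can over-correct. Step 7 confirms this for a residualised AUC. It argues against basing the claim on the adjusted AUC alone, not against reporting the added value.

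Nor do the documents show that the pilot AUC of 0.98 (20 patients, section 1.3.4) was an exposure effect; they give no session counts for it.

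**Conclusion.** The concern holds in a limited form. The timing, the response-dependent course length and the absence of session count and arm from 5.8.4 are all in the text. Given an association between SSI and HRSD-24 remission and a correlation of 0.3 to 0.7 between LICI change and sessions, exposure alone yields an AUC of roughly 0.54 to 0.70. That is often enough for nominal significance and rarely enough for the 0.85 level. If either link is absent, the bias disappears; if exposure moves LICI against the true effect, a real signal could be hidden.

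The baseline-entropy ROC is outside the point. Hypothesis (2) in section 3.0 and the ROC in 5.8.5 describe different predictors and should be reconciled. This is a tertiary aim, and no primary or secondary result is touched. The gap concerns what a positive biomarker finding can be said to show.

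**What to change.** In 5.8.4, and in any entropy-change analysis under 5.8.5, keep the unadjusted AUC and report beside it:

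1. the AUC of session count alone;
2. the AUC gained by adding LICI (or entropy) change to a model with session count, days between recordings and arm, with a confidence interval;
3. results by arm, which also matches hypothesis (1), since it concerns MST.

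Describe a finding as target engagement only if LICI change adds to session count and arm. Do not hold a residualised AUC alone to the 0.85 level, because it is conservative. State whether the entropy predictor is the baseline level or the change. Benzodiazepine dose is an optional further covariate and not part of this point.

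The cost is SAP wording and a few extra model fits. Session counts are needed anyway to apply the stopping rule, and recording dates should be on file. No visit, recording or treatment changes. The downside is a more cautious claim if session count lies partly on the path from LICI change to response, which is why both results are shown.
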